13.1 CRITERIA FOR REMOVAL FROM STUDY

Study treatments will be discontinued for all patients in the following situations:

- Disease progression
- General or specific changes in the patient's condition render the patient unacceptable for further treatment in the judgment of the investigator
- Unacceptable adverse event(s)
- Inability of patient to comply with study requirements

In addition to the above, patients may withdraw from the study at any time for any reason. Once decision has been made to stop study drug treatment, the treating physician will report on the date of last treatment and the reason for cessation of study drug treatments. Patients who are no longer receiving study drugs will still be followed clinically for toxicity and survival endpoints, unless the patient explicitly declines.

Procedures for Study Withdrawal

Withdrawal procedures will include an end-of-treatment (EOT) visit within 30 days of the last dose of study drug.

Replacement of Patients

During both Phase I and II of the study (dose-escalation), any patient who discontinues treatment before completing the first cycle of treatment (C1D21) will be considered not evaluable for DLT and will be replaced. Completion of the first cycle of treatment is defined by completion of at least 75% of both study drugs during the initial 28-Day DLT evaluation window (7-day safety run-in + 21-day Cycle 1). The only exception are patients who are unable to complete at least 75% of the prescribed dose of DS-3201b and irinotecan during the DLT evaluation period (safety run-in + Cycle 1) due to non-disease-related \geq Grade 2 adverse events; these patients will be considered to have a DLT and will not be replaced. Please see Section 11.0 for the full definition of DLTs.

During Phase II of the study, any patient who discontinues treatment before completing two cycles of treatment but has completed the DLT evaluation period will still undergo the first repeat CT scan prior to their scheduled C3D1. If a CT scan evaluation is unable to be obtained, these patients will not be replaced, and they will be considered as not deriving clinical benefit from the study drug.

Re-screening of Patients

Any patient who fails to meet eligibility criteria upon initial screening can undergo re-screening at a later time. The initial screening information, including the reason why the subject was initially ineligible, will be recorded. No data from the initial evaluation will be entered into the clinical database for patients who undergo re-screening and are ultimately enrolled onto the study.

Continuation of Treatment for Patients

Any patient who continues to derive benefit from the study drug combination with either a partial response or stable disease will be eligible to continue study treatment until unacceptable toxicity or progression of disease.

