Although all toxicities will be closely monitored and graded throughout the entire study treatment, only toxicities occurring during Cycle 1 of treatment (initial 7-day safety run-in plus the first 21 days) that meet the definition of DLT will influence the determination of MTD. Any toxicity during Cycle 1 of treatment that meets the definition of DLT as described below, whether it is attributed to either DS-3201b or irinotecan or both, will affect the determination of MTD during the Phase I portion of the study.

Dose-limiting toxicity (DLT) is defined as a clinically significant non-hematologic treatment-emergent adverse event (TEAE) or abnormal clinical laboratory value that is clearly **NOT** related to disease progression, intercurrent illness, and occurring during the DLT evaluation period (safety run-in + Cycle 1) on study that meets any of the following criteria:

Hematologic dose-limiting toxicity is defined as any:

- All Grade ≥ 3 adverse event that are at least possibly related to study treatment with the following exceptions:
 - Grade 4 neutropenia lasting less than 7 consecutive days.
 - Grade 3 neutropenia without fever and/or infection where fever is an oral temperature $\geq 38.5^{\circ}\text{C}$.

- Grade 4 thrombocytopenia (platelet count<25,000/mm³) lasting less than 7 consecutive days. *However, a platelet count <10,000/mm³ at any time for any duration will count as a DLT.*
- Grade 3 thrombocytopenia without bleeding.

Non-Hematologic dose-limiting toxicity is defined as any:

- All Grade ≥3 adverse events that are at least possibly related to study treatment with the following exceptions:
 - Grade 3 aspartate aminotransferase AST (SGOT) or alanine aminotransferase (ALT) (SGPT) or bilirubin for ≤ 7 days.
 - Grade 3 or 4 nausea, vomiting, and diarrhea that do not require hospitalization or total parenteral nutrition (TPN) support and can be managed with supportive care to ≤ Grade 2 within 48 hours.
 - Electrolyte abnormalities that are corrected to ≤ Grade 2 within 24 hours.
 - Alopecia and study drug-related fever (without Grade 3 neutropenia) will not constitute DLT.
 - Any Grade 5 adverse event proven to be clearly and incontrovertibly related to disease progression or intercurrent illness and not possibly related to study drug DS-3201b.

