If the treating physician determines that a TEAE occurring during the DLT evaluation period which met the definition for DLT is due to underlying disease progression or intercurrent illness and NOT due to study drug effect from either DS-3201b and irinotecan, a final determination regarding DLT determination will be discussed with the study PI.

Patients who are unable to complete at least 75% of the prescribed dose (i.e., 21 days) of DS-3201b and irinotecan during the DLT evaluation period (safety run-in + Cycle 1) due to non-disease-related ≥ Grade 2 adverse events will be considered to have a DLT. These same DLT definitions detailed above in this section will also apply for the entire duration of the Phase II portion of the study as it pertains to the toxicity stopping rule (please see Section 14.0 for more details).

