14.0 BIOSTATISTICS

Dose-Escalation Phase I:

We will employ a standard 3-by-3 dose-escalation phase I study design to investigate the maximum tolerated dose (MTD) of DS-3201b in combination with fixed dose irinotecan. The study population for Phase I dose-escalation will include only patients who complete at least 1 full cycle of treatment (including the initial 7-day safety run-in and the complete 21-days of Cycle 1); only these patients will be considered evaluable for DLT and determination of the MTD. Patients who do not receive at least 1 full cycle of study drug for reasons other than toxicity and who also do not meet any definition of DLT will be excluded from analysis and will be replaced.

DS-3201b will be administered at the dose levels of 25%, 50%, 75%, 100%, 125% and 150% of the predicted MTD (200 mg daily). Patients will be assessed for toxicity weekly with cycle 1, and then on day 1 of each subsequent cycle. Although DLTs may occur at any point during treatment, only DLTs occurring during Cycle 1 of treatment (initial 7-day safety run-in plus the first 21 days) will necessarily influence decisions regarding dose escalation, expansion of a dose level, or evaluation of intermediate dose levels. Patients will be monitored on day 1 of each subsequent cycle of therapy for treatment emergent adverse events.

If none of the initial cohort of 3 has a DLT, the dose level will be escalated. If one of three patients has a DLT, that dose level will be expanded with 3 more patients. Dose escalation will stop if ≥ 2 DLTs are seen at a dose level, whether out of 3 or 6 patients. Please see section 11.5 for a full definition of DLTs. The MTD is defined as the highest dose level at which no more than 1 of the 6 patients at that level has a DLT. If no patient in the current 3-patient cohort has a DLT and the dose level is under final consideration for the MTD, an additional three patients will be treated at that level for confirmation. For the Phase I portion of this study, the minimum sample size is 4 patients, and the maximum sample size is 36 patients. The 6 patients treated at the established MTD in Phase I will also count as the initial 6 patients in the Phase II portion of the study.

The probability of escalation is as follows:

True DLT rate	5%	10%	15%	20%	25%	30%	40%	50%
Probability of escalation	0.97	0.91	0.81	0.71	0.60	0.49	0.31	0.17

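### Read literally, the Phase II replacement rule can leave an observed DLT out of the toxicity stopping rule when the patient stops Cycle 1 early for another reason

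*Combined protocol and SAP*

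**What the plan says.** **Section 13.1, Replacement of Patients (both phases).** The rule is that "any patient who discontinues treatment before completing the first cycle of treatment (C1D21) will be considered not evaluable for DLT and will be replaced". The threshold is then defined: "Completion of the first cycle of treatment is defined by completion of at least 75% of both study drugs", taken over the 28-day window of run-in plus Cycle 1. One carve-out follows: "The only exception are patients who are unable to complete at least 75% of the prescribed dose of DS-3201b and irinotecan" because of a non-disease-related adverse event of Grade 2 or higher. For them, "these patients will be considered to have a DLT and will not be replaced". Having already met a DLT definition is not mentioned.

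**Section 14.0, Dose-Escalation Phase I.** Patients short of a full cycle are dropped only if they stopped "for reasons other than toxicity and who also do not meet any definition of DLT will be excluded from analysis and will be replaced".

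**Section 14.0, Phase II.** The stopping boundaries are at least 2, 3, 3, 3 and 4 DLTs at 5, 10, 15, 20 and 25 patients. The table is indexed by recruited patients, and the rule runs for all of Phase II. Nothing is said about a replaced patient's DLT.

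**Section 11, Definitions of Dose-Limiting Toxicity.** "These same DLT definitions detailed above in this section will also apply for the entire duration of the Phase II portion of the study", with reference to the toxicity stopping rule.

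**The concern.** The two replacement rules differ. The Phase I text of Section 14.0 sets two conditions for dropping a patient: no toxicity reason for stopping, and no DLT definition met. Section 13.1 asks only whether the cycle was completed and, if not, whether an adverse event caused the shortfall. A patient can therefore have a DLT, stop for something else, and be labelled not evaluable for DLT.

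Dose escalation is finished (Sections 1.0 and 9.1), so the difference matters for Phase II, where the Phase I wording does not formally apply. The Phase II boundaries are small counts, and a safety rule that turns on one event should not depend on how staff at two sites read a replacement paragraph.

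**Working it through.** **1. Is there a patient whom the wording loses?** Take a possibly related Grade 3 non-hematologic event on C1D3 that fits none of the listed DLT exceptions. It is a DLT. It resolves, and the patient progresses or withdraws on C1D7, before the second irinotecan dose.
- DS-3201b: at most 7 run-in days + 7 = 14 of 28 days, or 50%.
- Irinotecan: 1 of 2 doses, or 50%.
- Both are below 75%, so the cycle is not complete under Section 13.1.
- Did the adverse event cause the shortfall? Even if DS-3201b had been held from C1D3 to C1D7, that is 5 days, and 23/28 = 82% would still have been reachable. The early stop caused the shortfall, so the exception does not apply.

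Read literally, this patient is not evaluable, is replaced, and the DLT is not counted.

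**2. Do the printed stopping probabilities reproduce?** Inputs: the Section 14.0 boundaries (2/5, 3/10, 3/15, 3/20, 4/25) and the six stated DLT rates. Method: exact binomial recursion over 25 patients, removing at each look the probability at or above the boundary.

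| True DLT rate | 0.05 | 0.09 | 0.13 | 0.17 | 0.21 | 0.25 |
|---|---|---|---|---|---|---|
| Printed | 0.09 | 0.30 | 0.54 | 0.74 | 0.87 | 0.94 |
| Recomputed | 0.090 | 0.301 | 0.541 | 0.736 | 0.865 | 0.938 |

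They reproduce at every rate, on the basis that every DLT is counted.

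**3. What happens if some DLT patients are removed and replaced?** Let p be the true DLT rate, f the share of DLT patients who are lost this way, and g the share of patients without a DLT who stop early for non-adverse-event reasons and are also replaced. The documents give neither f nor g; both are assumptions. The DLT rate among counted patients is

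p(1−f) / [p(1−f) + (1−p)(1−g)].

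With g = 0 this reduces to p(1−f)/(1−pf). For example, p = 0.17 and f = 0.20 give 0.136/0.966 = 0.1408. Putting the counted rate through the same recursion gives these stopping probabilities:

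| Assumption | p = 0.17 | p = 0.21 | p = 0.25 |
|---|---|---|---|
| No loss | 0.736 | 0.865 | 0.938 |
| f = 5%, g = 0 | 0.706 | 0.843 | 0.925 |
| f = 10%, g = 0 | 0.674 | 0.818 | 0.908 |
| f = 20%, g = 0 | 0.600 | 0.757 | 0.866 |
| f = 10%, g = 5% | 0.705 | 0.842 | 0.924 |
| f = g (any value) | 0.736 | 0.865 | 0.938 |
| f = 10%, g = 15% | 0.77 | 0.89 | 0.95 |

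When f = g the factors cancel and the counted rate is p. When g exceeds f, the trial stops more often than printed.

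**4. Effect on a single decision.** Two DLTs in the first 5 patients meet the boundary. If one of them is declared not evaluable, one remains and the trial continues.

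**The case against.** **The Phase II text already points to counting these DLTs.** The boundary is indexed on recruited rather than evaluable patients, and the DLT definitions apply throughout Phase II for this rule. No sentence says that an observed DLT is deleted. This stands as a reasonable reading, and it means that Section 13.1 is not the only Phase II text on the matter. But no Phase II sentence says that such a DLT counts, and Section 13.1, which names both phases, declares the patient not evaluable for DLT.

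**Most DLT patients are safe.** This also stands. A patient stopped by the DLT itself falls under the exception, and one who reaches 75% has completed the cycle. A tempting example is a platelet count below 10,000/mm³ on C1D10 with a stop for progression on C1D14, because "a platelet count <10,000/mm³ at any time for any duration will count as a DLT". It probably fails. If dosing ran through C1D14, the patient took 7 + 14 = 21 of 28 DS-3201b days (75%) and both irinotecan doses, which is completion. If DS-3201b was interrupted as Table 5.0 directs, the missed doses point to the exception.

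**The loss of stopping probability is not established.** A reader might infer that the rule stops less often than printed. That needs DLT patients to stop early for other reasons more often than patients without a DLT, and nothing in the documents supports it. Multiplying the DLT rate by (1−f) would overstate the loss, because it keeps the patient in the count as DLT-free when Section 13.1 says the patient is replaced. Replacement also concerns only the 28-day window, so DLTs in later cycles cannot be lost this way; applying f to all DLTs is therefore on the high side.

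**Conclusion.** The point holds as a narrow gap in the rules. Followed literally, Section 13.1 drops a Phase II DLT when three things coincide: a DLT definition is met in the 28-day window, less than 75% of dose is taken, and the shortfall is not due to a non-disease-related Grade 2 or higher adverse event. Sections 11, 13.1 and 14.0 do not settle the matter between them.

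The printed operating characteristics are right. The certain consequence is that one such patient can turn a stop into a continuation. The average effect is unknown. With only DLT patients removed and an assumed loss of 5% to 20%, the stopping probability becomes 0.706 to 0.600, 0.843 to 0.757 and 0.925 to 0.866 at true rates of 0.17, 0.21 and 0.25. With equal early stopping in both groups it does not change. The documents do not support a general claim that the rule is less protective than stated.

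**What to change.** Reconcile Section 13.1, both parts of Section 14.0 and the DLT definitions in Section 11 by carrying the Phase I condition into the Phase II replacement rule:
- Not evaluable for DLT, and replaced, should cover only patients who stop before completing Cycle 1 and have met no DLT definition.
- Any patient who has met a DLT definition counts in the Section 14.0 stopping rule and is not replaced as not evaluable for DLT, whatever the reason for stopping.

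The Phase II text of Section 14.0 should repeat this and say whether a replaced patient without a DLT counts toward the number recruited at each look.

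The cost is a sentence or two. No new data are needed, since Section 13.1 already has patients off study drug followed for toxicity. Boundaries, sample size and printed probabilities stay as they are.

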14.0 BIOSTATISTICS

Dose-Escalation Phase I:

We will employ a standard 3-by-3 dose-escalation phase I study design to investigate the maximum tolerated dose (MTD) of DS-3201b in combination with fixed dose irinotecan. The study population for Phase I dose-escalation will include only patients who complete at least 1 full cycle of treatment (including the initial 7-day safety run-in and the complete 21-days of Cycle 1); only these patients will be considered evaluable for DLT and determination of the MTD. Patients who do not receive at least 1 full cycle of study drug for reasons other than toxicity and who also do not meet any definition of DLT will be excluded from analysis and will be replaced.

DS-3201b will be administered at the dose levels of 25%, 50%, 75%, 100%, 125% and 150% of the predicted MTD (200 mg daily). Patients will be assessed for toxicity weekly with cycle 1, and then on day 1 of each subsequent cycle. Although DLTs may occur at any point during treatment, only DLTs occurring during Cycle 1 of treatment (initial 7-day safety run-in plus the first 21 days) will necessarily influence decisions regarding dose escalation, expansion of a dose level, or evaluation of intermediate dose levels. Patients will be monitored on day 1 of each subsequent cycle of therapy for treatment emergent adverse events.

If none of the initial cohort of 3 has a DLT, the dose level will be escalated. If one of three patients has a DLT, that dose level will be expanded with 3 more patients. Dose escalation will stop if ≥ 2 DLTs are seen at a dose level, whether out of 3 or 6 patients. Please see section 11.5 for a full definition of DLTs. The MTD is defined as the highest dose level at which no more than 1 of the 6 patients at that level has a DLT. If no patient in the current 3-patient cohort has a DLT and the dose level is under final consideration for the MTD, an additional three patients will be treated at that level for confirmation. For the Phase I portion of this study, the minimum sample size is 4 patients, and the maximum sample size is 36 patients. The 6 patients treated at the established MTD in Phase I will also count as the initial 6 patients in the Phase II portion of the study.

The probability of escalation is as follows:

True DLT rate	5%	10%	15%	20%	25%	30%	40%	50%
Probability of escalation	0.97	0.91	0.81	0.71	0.60	0.49	0.31	0.17

Adverse events will be graded according to the CTCAE version 5.0, with patients being assessed weekly while on the treatment. Data on pharmacokinetics (PK) of DS-3201b after DS-3201b administered alone or in combination with irinotecan will be collected 7 Days prior to C1D1, on C1D1, on C1D8, on C1D15 and on C2D15 for each patient in the phase I component of this study. Standard plasma PK parameters for each of the above timepoints will include the maximum plasma concentration (Cmax), minimum plasma concentration (Cmin), and time to maximum plasma concentration (Tmax). The area under the plasma concentration versus time curve (AUC) for DS-3201b will be estimated using non-compartmental analysis and/or a population PK approach.

Phase II:

The second phase of this study will be an open-label, single arm, phase II study of DS-3201b at the established RP2D in combination with fixed dose irinotecan. The primary objective of this study is to assess efficacy, ORR defined as CR+PR measured by RECIST v1.1.

Historical control:

We base the sample size calculation on the estimated response rate of 16% as a benchmark, which we derive from the reported study from Le Chevalier et al.³⁰ A two-stage Simon's minimax design will be employed to test the null hypothesis that the true ORR is 16% versus the alternative hypothesis that the true ORR is at least 35% with a type I error of 0.05 and a power of 0.8. In the first stage, 16 patients will be accrued. The first 6 patients out of this initial 16-patient cohort will be the 6 patients treated at MTD in Phase I.

Efficacy will be measured by RECIST v1.1 assessed response to therapy. If there are 2 or fewer responses in these 16 patients, the study will be stopped early for futility. The probability of stopping the study early for futility is 52% per the two-stage Simon's minimax design. If at least 3 patients show response in this first stage, we will request permission from the sponsor to enroll an additional 15 patients in the second stage. At the end of the study, if ≥ 9 patients out of total of 31 enrolled patients show a partial response or a complete response, then further investigation of DS-3201b in combination with irinotecan will be considered worthwhile.

Study enrollment of the 17th patient will be suspended until the determination of the first-stage results, unless the benchmark of 3 patients with radiographic response is achieved by then. All patients will be included in the primary analysis, even if there are major protocol deviations. Patients are considered non-responses (PD) if they are not evaluable (including if CT scan evaluation not available) or died during the study. This study requires accrual of a minimum of 16 patients and up to a maximum of 31 patients if the cohort is expanded to the second stage. The accrual time is estimated to be between 10-24 months at the rate of 3 patients per month and a likely planned 4 months suspension between the first and second stages of this Phase II study.

To protect patients from excessive toxicity, a stopping rule for toxicity will be implemented during Phase II. Since the 6 patients treated at RP2D in Phase I will be included in the Phase II portion of the study, the early stopping rule for toxicity is calculated based on 31-

6=25 newly recruited patients. This toxicity rule will apply for the entire duration of the Phase II portion of the study.

Stopping rule:

Number of recruited patients	5	10	15	20	25
Number of DLT to stop the trial	≥2	≥3	≥3	≥3	≥4

Operating characteristics of the stopping rule:

True DLT rate	0.05	0.09	0.13	0.17	0.21	0.25
Probability of stopping the trial	0.09	0.30	0.54	0.74	0.87	0.94

The ORR is defined as the proportion of patients with CR, or PR at any reassessment after start based on RECIST v1.1 criterion. The time frame for evaluating the primary endpoint of ORR for this portion of the study will be 6 months from the date of Cycle 1 Day 1 for each patient. The ORR and corresponding exact 95% CI will be reported. Progression-free survival will be measured from the start of treatment until the documentation of disease progression or death due to any cause, whichever occurs first, and censored on the date of last tumor assessment. In addition, we will document absence of tumor progression for patients who are still alive prior to data cutoff, dropout, or the initiation of alternate anticancer treatment. Overall survival will be determined as the time from the start of DS-3201b treatment to death, and censored on the last follow-up date. PFS and OS will be evaluated using the Kaplan-Meier method. The duration of response (for those with CR or PR) and durable of stable disease while on treatment (for those with SD) will also be evaluated using the Kaplan-Meier method.

All recorded toxicity data and adverse events of DS-3201b will be listed and tabulated by system organ class, preferred term and treatment. Any significant vital signs and clinical laboratory test results will be listed and summarized. Any significant physical examination findings and clinical laboratory results will be listed.

As secondary objectives, we will explore downstream mechanistic biomarkers of DS-3201b including SLFN11 expression and H3k27me3 signature by descriptive and graphical summaries of assays performed on tissue samples obtained during the study. The Wilcoxon rank sum test will be used to assess SLFN11 expression by immunohistochemistry as a potential predictive biomarker of response to DS-3201b and to correlate with trimethylation of H3K27 as measured by immunohistochemistry in pretreatment, on-treatment and post-treatment tissue samples as well as in circulating tumor cells (CTCs). In addition, next-generation sequencing (NGS) will also be performed on pre-treatment, on-treatment and post-treatment tissue samples obtained from the study. This data will be analyzed using descriptive

and graphic summaries of the assays performed, including use of gene expression heat maps and advanced computational biostatistics with collaborators in the [name] laboratory.

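### Patients replaced for DLT evaluability may be left out of the ORR set, which could bias the response rate upward; Sections 13 and 14.0 do not settle whether they count

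*Combined protocol and SAP*

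**What the plan says.** **Replacement.** Section 13 (Replacement of Patients) says that a patient who stops before completing the first cycle is not evaluable for DLT and is replaced. It names both Phase I and Phase II. Completion means at least 75% of both drugs over the 28-day window (7-day run-in plus 21-day Cycle 1). Patients who fall short because of non-disease-related adverse events of Grade 2 or higher count as DLTs and are not replaced.

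**Exclusion.** Section 14.0 (Dose-Escalation Phase I) goes further. "Patients who do not receive at least 1 full cycle of study drug for reasons other than toxicity", and who have no DLT, are excluded from analysis as well as replaced.

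**Carry-over.** The same section adds: "The 6 patients treated at the established MTD in Phase I will also count as the initial 6 patients in the Phase II portion". Its Phase II part repeats this for stage 1: "The first 6 patients out of this initial 16-patient cohort will be the 6 patients treated at MTD in Phase I".

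**Primary analysis.** Section 14.0 (Phase II) states: "All patients will be included in the primary analysis, even if there are major protocol deviations". Patients who are not evaluable, including those without a CT evaluation, are non-responses.

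**Design.** "A two-stage Simon's minimax design will be employed", with a null ORR of 16%, an alternative of 35% or more, and "with a type I error of 0.05 and a power of 0.8". The trial stops if there are 2 or fewer responses in 16 patients and succeeds with 9 or more in 31.

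**The concern.** Replacing early dropouts is sound for counting DLTs, since a patient who leaves early for other reasons says little about toxicity. It is not sound for a response rate, because leaving early is related to the outcome.

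Scans are scheduled after every two cycles (Table 3.0, footnote 4; Section 12.0). Section 13 asks for a scan before C3D1 from Phase II patients who stop before two cycles, but only if they have completed the DLT period. A patient replaced before that point would therefore normally have no post-baseline scan, and would be a non-response under the all-patients rule. Taking such patients out and filling their places with patients who got further can in practice only raise the ORR.

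At stake are the two decisions that the design makes: whether to continue after 16 patients, and whether the combination merits further study after 31.

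**Working it through.** **1. The plan's own design.** Inputs from Section 14.0: n1 = 16, stop if X1 ≤ 2; N = 31, success if X1 + X2 ≥ 9; null 0.16; alternative 0.35.

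- Futility stop at p = 0.16: 0.84^16 + 16(0.16)(0.84^15) + 120(0.16²)(0.84^14) = 0.0614 + 0.1873 + 0.2675 = 0.516. The plan states 52%.
- P(success) = Σ (x = 3 to 16) P(X1 = x) × P(X2 ≥ 9 − x), with X1 ~ Bin(16, p) and X2 ~ Bin(15, p). This gives 0.0474 at p = 0.16 and 0.801 at p = 0.35.

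The stated design reproduces. A search over two-stage designs confirms it as the minimax one. Headroom under 0.05 is 0.05 − 0.0474 = 0.0026.

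**2. Effect of leaving replaced patients out.** Let q be the fraction of patients at the RP2D who are replaced, and assume that none of them would respond. The documents give no value for q. Patients who remain after the filter then have a null response probability of 0.16/(1 − q): 0.178 at q = 10% and 0.200 at q = 20%.

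- *Only the six filtered:* X1 ~ Bin(6, 0.16/(1 − q)) + Bin(10, 0.16); X2 ~ Bin(15, 0.16).
- *All 31 filtered:* every patient has probability 0.16/(1 − q). This applies if the Phase II replacement rule in Section 13 also removes patients from the ORR.

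| Assumed q | Type I error, six filtered | Futility stop, six filtered | Type I error, all 31 filtered | Futility stop, all 31 filtered |
|---|---|---|---|---|
| 0% | 0.047 | 0.516 | 0.047 | 0.516 |
| 5% | 0.050 | 0.502 | 0.063 | 0.479 |
| 10% | 0.053 | 0.487 | 0.083 | 0.439 |
| 15% | 0.057 | 0.470 | 0.110 | 0.397 |
| 20% | 0.062 | 0.451 | 0.147 | 0.352 |
| 25% | 0.067 | 0.430 | 0.195 | 0.305 |

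Type I error crosses 0.05 at q of about 4.7% when only the six are filtered, and at about 1% when all 31 are.

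**3. Shift in the expected ORR under the null, six filtered.** (6 × 0.16/(1 − q) + 25 × 0.16)/31 is 16.3% at q = 10% and 16.8% at q = 20%, against 16%.

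**4. What the documents say about q.** Only that Phase I enrolled 12 patients and settled on 100 mg. If the 12 include replaced patients, and six evaluable patients at 100 mg and at least three at a higher level are taken off, at most 12 − 6 − 3 = 3 remain. That is a rough ceiling of 3 of 9 at 100 mg, and the number may be zero.

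**The case against.** The strongest reply is that the all-patients rule already answers the point. It is not limited to newly recruited patients, and it makes non-evaluable patients non-responses. The exclusion in the Phase I text follows directly on the definition of DLT evaluability, so it may mean exclusion from the DLT analysis only. On that reading replaced patients stay in and there is no bias.

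This reading is possible, but the text does not secure it. The plan provides for exactly six Phase I patients: the Protocol Summary takes six from Phase I and allows 25 unique Phase II patients, and Section 14.0 computes 31 − 6 = 25. A seventh patient treated at the RP2D and then replaced has no place in the 16 or the 31.

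Three stronger readings are tempting, and the documents do not support them.

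- *The ORR is biased and the 5% level is not held.* No replacement count is given. With only the six filtered, 0.05 is passed only above about q = 5%, and the excess is small at 10% to 20%. Eligibility (life expectancy of at least 12 weeks; KPS of at least 70% or ECOG 0 to 2) argues against high values of q, without excluding them.
- *The six are filtered while the 25 new patients follow the opposite rule.* Section 13 names Phase II in its replacement rule, and the all-patients rule covers everyone. The conflict is the same for both groups.
- *The six are all full-cycle completers.* Patients who stop for toxicity stay in as DLTs. Section 13 sets completion at 75% of dosing, so a patient with both irinotecan doses and 21 days of DS-3201b has completed. The filter is on stopping treatment early, not on progression within 28 days.

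**Conclusion.** The replacement and exclusion rules conflict with the all-patients rule, and following the former as written can raise the ORR. The size depends on an unreported number. If nobody was replaced, the bias is zero. If only the six are filtered, the effect is modest: type I error 0.053 to 0.062 and futility stop 0.49 to 0.45 for q of 10% to 20%. If Phase II replacements also leave the ORR, it is material: type I error 0.083 to 0.147 over the same range. These figures assume that replaced patients would not have responded and that the 2/16 and 9/31 cut-offs are applied unchanged. The point deserves correction because the design has almost no headroom and the remedy is cheap. It does not show that the trial's error rate has been exceeded.

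**What to change.** In Sections 13 and 14.0:

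1. State that replacement affects DLT evaluability only, in both phases.
2. Define the ORR set as every patient who received DS-3201b at the RP2D, taken in enrolment order across Phase I and Phase II. The 16th such patient closes stage 1 and the 31st closes the final analysis. Those without a post-baseline scan count as non-responses.
3. Report how many patients were replaced at the RP2D in each phase.

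If the six are already fixed, add a sensitivity analysis that applies the 3/16 and 9/31 rules to the first 16 and first 31 patients treated at the RP2D in enrolment order. Also report the ORR with its exact CI among all patients treated at the RP2D. Adding replaced patients on top of the fixed sets would not do: the response count could not fall, and the cut-offs would be applied to samples larger than the 16 and 31 for which they were derived.

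With this definition the design figures return to 0.047, 0.801 and 0.516. The cost is a few sentences and a small re-count, with no increase in the 31 patients in the ORR set. The ORR may come out slightly less favourable. If the number replaced is zero in both phases, one sentence saying so closes the point.
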